10.4.1.4 Spain: Information System for the Development of Primary Care Research

The information system for the development of primary care research database (*Sistema d'Informació per al Desenvolupament de la Investigació en Atenció Primària* [SIDIAP]), was established in 2010 and is under the organisation of the Catalan Institute of Health and the Primary Care Research Institute Jordi Gol. The SIDIAP database is frequently used for research purposes, and it includes a representative sample of patients attended by general practitioners. It is a regional register covering approximately 6 million people (around 80% of the individuals living in the Catalan region), which represents about 10.2% of the total Spanish population.

The SIDIAP data consists of primary care electronic medical records as well as other complementary databases with data available from 2006. Health care information is entered automatically into the e-records software (e-CAP). Since e-CAP is used by the most important health providers of the Catalan Health Department, SIDIAP is representative of both the urban and

rural areas of Catalonia. Individuals enter the SIDIAP database at birth or immigration and exit by death or emigration.

Information on all prescribed and dispensed drugs is obtained from the joint database of CatSalut with Catalan pharmacies. Drug indications are available for a few drugs which registration of the indication is required. Dose and DDDs are available in pharmacy invoice records. Dates of prescription are available for reimbursed drugs obtained in pharmacies. Other data sources can be linked to the SIDIAP data providing additional information, such as hospital admissions (from the *conjunt mínim de dades bàsiques d'hospitalització*), hospital outpatient medications (*Medicació Hospitalària de Dispensació Ambulatòria* [MHDA]) and the mortality register from which causes of death can be retrieved.

The database includes information on physician visits (date and type), diagnoses, results of laboratory analyses, as well as lifestyle factors such as history of smoking and BMI.

In the SIDIAP database, the length of data lag is approximately 6 months, and the database is updated twice a year (January and July). The time lag between when care is given and its capture in the data source is normally 6 months. Prior to data extraction, ethical approval and data holder permits must be obtained. The SIDIAP will perform scientific and ethical review and it will perform the data analysis locally.

Study-specific data

Anifrolumab use is expected to be captured, as data on biologics (including IV belimumab use) are available in SIDIAP since 2010 through hospital outpatient medications. Data on SLE SOC exposure are available.

Data on malignancies (overall and sub-types) and serious infections (overall and sub-types) are available. Infection diagnosis and date of death are available. Previous infections may be available if the diagnosis occurred in primary care.

Data on covariates are generally available (Table 26), including data for BMI, alcohol consumption, and smoking. Alcohol consumption and smoking are coded using internal codes. Data on procedures with radiation exposure are not available.

10.5 Study size

10.5.1 Expected number of SLE patients exposed to anifrolumab

Due to the recency of anifrolumab approval in the EU (14 February 2022), data on its uptake in the selected data sources for the duration of the study enrolment period (up to April 2025 for serious infections, and May 2028 for malignancies) is not available. Therefore, estimates of the number of expected anifrolumab patients in each data source for each year of the study were made based on country-level assumptions of the prevalence of SLE, proportion of patients with moderate to severe SLE, proportion of patients who have non-renal SLE, proportion of non-renal SLE

patients who are treated, a gradual uptake of anifrolumab from 1% in the initial years after market approval to 13-16% in 2028 and population coverage of each selected data source. Details of these assumptions and the annual number of exposed patients in each data source are provided in Appendix 4.3. Number of SLE patients exposed to anifrolumaband Table 27.

The average number of patients with SLE expected to be identified in the data sources every year (potential pool of comparators) and the total number of new patients exposed to anifrolumab identified during the enrolment period in each study cohort and data source are summarised in Table 8. For the serious infections and malignancies' cohorts, 1,435 and 3,506 patients newly exposed to anifrolumab may be captured, respectively⁸.

Table 8 Expected size of the SLE population exposed to anifrolumab in the selected data sources

Country data	Average number	Expected number of patients initiating anifrolumab				
Country, data source	of SLE patients per year ^a	Malignancies' cohort (Enrolment: 2022-2028)	Serious infections' cohort (Enrolment: 2022-2025)			
Denmark, National Registers	1,122	183	89			
France, SNDS	15,501	2,695	1,005			
Germany, SHI	1,224	216	126			
Spain, SIDIAP	2,944	412	216			
All		3,506	1,435			

Abbreviations - SHI: Statutory Health Insurance; SIDIAP: System for the development of primary care research database; SLE: systemic lupus erythematosus; SNDS: National Health Data System

^aEstimated as the annual average number of patients in each data source with moderate to severe, non-renal SLE treated with SLE SOC for the period 2022 to 2028 (more details in Appendix 4.3. Number of SLE patients exposed to anifrolumab).

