10.2.1 Study time periods

The study time period for analysis will be based on availability of information from the data sources and on the date of market availability for anifrolumab. The **start of the study period** will be the market launch date of anifrolumab in each country (Table 3); this considers that all data sources included in the study are available for at least 12 months before that date (12 months correspond to the minimum look-back period before index date for confounders and/or risk factors).

The **end of study period**, defined as the last possible day of follow-up when all patients still in the study are censored, will likely differ between countries and will depend on length of data lag in each country at the time when the last data extraction is performed (Table 3). The rationale for this choice is to include all data available from relevant data sources to capture a sufficient number of outcomes and exposures for the primary outcomes at study.

Country	Start of study	Start of	End of	End of	End of study	End of study
	period ^a	enrolment ^b	enrolment for	enrolment	period for SI	period for M
		Date when first	SI outcomes ^c	for M	outcomes ^e	outcomes ^f
		patient can be	Date when last	outcomes ^d	Last possible	Last possible
		enrolled	patient can be	Date of last	day of	day of follow-
			enrolled	patient	follow-up,	up, when all
				enrolled	when all	patients still
					patients still	active are
					included are	censored
					censored	
Denmark	04 May 2022	04 May 2022	30 April 2025	31 May 2028	31 May 2025	31 May 2029
France	19 April 2022	19 April 2022	30 April 2025	31 May 2028	31 May 2025	31 May 2029
Germany	11 March 2022	11 March 2022	30 April 2025	31 May 2028	31 May 2025	31 May 2029
Spain	May 2023 (Tbc)	May 2023 (Tbc)	30 April 2025	31 May 2028	31 May 2025	31 May 2029

Table 3 Relevant dates of the study by country

Abbreviations: SI, serious infection; M, malignancy; Tbc, to be confirmed.

^aAnifrolumab market launch date.

^bStart of enrolment is same for the serious infections and malignancy cohorts.

°For infections the last patient will be included 1 month before the end of study period.

^dFor malignancies the last patient will be included 12 months before the end of study period.

^eCalculated assuming that the final report is due on 30 Nov 2028, assuming a two-year lag time in data availability. Needs to be adapted by country after feasibility study.

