Considering the estimated number of patients initiating anifrolumab during the study period (3,506 for the malignancies cohort, and 1,435 for the serious infections cohort Table 8) and the required sample size presented above (3,195 for the malignancies cohort and 1,312 for the serious infections

cohort), there is a reasonable assumption that the final study report milestones as specified in this protocol can be met. However, the assumptions used in the calculation of the exposed anifrolumab patients will be evaluated at the first progress report (31 May 2026) and first interim report (31 May 2027). If the assumptions do not hold, the final study report milestones will be re-evaluated, and potential mitigation steps will be explored.

each data source)											
Country	Share of	Minimum required sample size	Minimum required sample size								
	country in	(anifrolumab patients) for the	(anifrolumab patients) for the SI								
	study (%)	Malignancy outcome with IR = 6.31	outcome with IR = 39.8 per 1000 py								
		per 1000 py									
Denmark	5.89%	188	77								
France	74.56%	2,382	978								
Germany	5.40%	173	71								
Spain	14.16%	452	186								
Total	100.00%	3,195	1,312								

Table 13 Minimum sample size needed for malignancy and SI outcomes (overall and in each data source)

Abbreviation - HR: hazard ratio; IR: incidence rate; SD: standard deviation

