coverage)	Number of SLE patients initiating anifrolumabe	14	19	27	29	36	35	23		183	8 9
	Country-level]		
France,	Number of patients with SLE ^b	14,772	15,066	15,066	15,066	16,550	16,584	16,616]		
SNDS	Expected anifrolumab uptake (%)	0%	2%	4%	7%	11%	14%	16%]		
(98.9%	Data source estimates									J I	
population	Number of patients with SLE ^c	14,609	14,900	14,900	14,900	16,367	16,401	16,433	15,501	J I	
coverage)	Number of SLE patients exposed to anifrolumab ^d	<10	226	536	1,005	1,865	2,299	2,695			
	Number of SLE patients initiating anifrolumabe	<10 ^f	226	310	469	860	434	396		2,695	1,005
	Country-level								Į		
Germany,	Number of patients with SLE ^b	22,347	22,321	22,285	22,259	22,234	22,222	22,173	ļ		
SHI	Expected anifrolumab uptake (%)	1%	3%	7%	10%	13%	16%	18%	Į		
(5.5%	Data source estimates										
population	Number of patients with SLE ^c	1,229	1,227	1,225	1,224	1,222	1,222	1,219	1,224		
coverage)	Number of SLE patients exposed to anifrolumab ^d	15	41	80	126	163	200	216			
	Number of SLE patients initiating anifrolumabe	15	26	40	45	37	37	16		216	126
	Country-level								ļ		
Spain,	Number of patients with SLE ^b	27,713	27,689	27,660	27,628	30,166	30,467	30,772	Į		
SIDIAP	Expected anifrolumab uptake (%)	0%	2%	5%	8%	8%	12%	13%]		
(10.2%	Data source estimates]	
population	Number of patients with SLE ^c	2,826	2,824	2,821	2,818	3,076	3,107	3,138	2,944]	
coverage)	Number of SLE patients exposed to anifrolumab ^d	<10	46	129	216	235	363	412			
	Number of SLE patients initiating anifrolumab ^e	<10 ^f	46	83	86	20	128	49		412	216
						Total nu	mber of n	ew anifro	lumab patients	3,506	1,435

Abbreviations: M, malignancy; SHI: Statutory Health Insurance; SIDIAP: System for the development of primary care research database; SLE: systemic lupus erythematosus; SNDS: National Health Data System; SI, serious infection

^a Estimated as the average number of patients with SLE in the data source from 2022 to 2028

^b Based on 12-month prevalence estimate. Estimate provided is the number of patients with non-renal, moderate to severe SLE who receive pharmacological treatment

^c Number of SLE patients in the country multiplied by the coverage of the data source

^d Number of SLE patients in the data source multiplied by the anifrolumab uptake

e Number of SLE patients exposed to anifrolumab in the current year minus the number of SLE patients exposed to anifrolumab in the previous year

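### The 1,435 expected serious-infection patients include all of 2025, but enrolment closes on 30 April 2025; with even accrual the count is about 1,012, against 1,312 required

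*Protocol*

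**What the plan says.** Section 10.5.1 describes the enrolment period as running "up to April 2025 for serious infections, and May 2028 for malignancies". Table 3 gives 30 April 2025 as the last SI enrolment date in all four countries and 31 May 2025 as the end of SI follow-up. Its footnote explains: "For infections the last patient will be included 1 month before the end of study period".

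Table 8 is introduced as the number of new anifrolumab patients identified during the enrolment period, and the text sums it up for the SI and malignancy cohorts in turn: "1,435 and 3,506 patients newly exposed to anifrolumab may be captured". Its SI column is labelled 2022-2025 and totals 1,435. The source is Table 27 in Appendix 4.3, where annual initiators are defined as "Number of SLE patients exposed to anifrolumab in the current year minus the number of SLE patients exposed to anifrolumab in the previous year". These are calendar-year counts, and no part-year adjustment is mentioned.

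Section 10.5.2 sets 1,435 against the required 1,312 and concludes that "there is a reasonable assumption that the final study report milestones as specified in this protocol can be met". Section 7 also says that the required SI size is estimated to be attained, on the uptake assumptions.

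**The concern.** The expected count and the enrolment window refer to different end dates, eight months apart. Uptake is modelled as rising, so the year that is only partly open to enrolment is also the largest: 2025 supplies about 44% of the SI total (629/1,435). The stated surplus over the requirement is only 123 patients (1,435 - 1,312), or about 9%.

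Serious infection is a primary safety outcome. If the expected number is overstated, the regulator is told that 80% power is within reach when the protocol's own figures do not show it, and a null result from a smaller cohort could be read as more reassuring than it is.

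**Working it through.** **Inputs.** Annual initiators and patients exposed, from Table 27. The two cells for 2022 shown as <10 are taken as 0, as the protocol's own totals imply.

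| Source | 2022 | 2023 | 2024 | 2025 | Sum 2022-25 | Exposed, 2024 |
|---|---|---|---|---|---|---|
| Denmark | 14 | 19 | 27 | 29 | 89 | 60 |
| France | <10 | 226 | 310 | 469 | 1,005 | 536 |
| Germany | 15 | 26 | 40 | 45 | 126 | 80 |
| Spain | <10 | 46 | 83 | 86 | 215 | 129 |
| All | 29 | 317 | 460 | 629 | 1,435 | 805 |

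**Reproducing the plan's figure.** 89 + 1,005 + 126 + 215 = 1,435, an exact match, reached only with the whole of 2025 included. (Table 8 shows 216 for Spain, so its column adds to 1,436; this is rounding and nothing turns on it.)

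**Count to 30 April 2025.**
- Even accrual by days: 805 + 629 x 120/365 = 1,012. By months: 805 + 629 x 4/12 = 1,015.
- Early 2025 at the 2024 pace: 805 + 460/3 = 958.
- Adding 9 for each of the two <10 cells: 805 + 18 + 629/3 = 1,033.
- Shortfall at 1,012: (1,312 - 1,012)/1,312 = 22.9%.
- Share of 2025 initiators needed by 30 April to reach 1,312: (1,312 - 805)/629 = 507/629 = 80.6%, where even accrual would give about 33%.

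**Power.** Table 12, 39.8 per 1000 person-years, HR 1.5, 1:3 matching, linear interpolation between 1,000 and 1,500 exposed:
- SD 0.2: 0.716 + (12/500) x (0.835 - 0.716) = 0.719.
- SD 0.1: 0.789 + (12/500) x (0.882 - 0.789) = 0.791.
- Check of the method at 1,312, SD 0.2: 0.716 + (312/500) x 0.119 = 0.790, close to the stated 0.80.

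A separate simulation of the design (four sources with Table 13 shares, 2 years, log-scale SD 0.132, random-effects inverse-variance pooling, 20,000 runs) gave 0.792 at 1,312 and 0.744 at 1,015. It agrees with the plan's requirement and confirms a loss of power, of about 5 points rather than 7.

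**Malignancy, for comparison.** Table 27 counts all of 2028, while enrolment ends on 31 May 2028. Initiators in 2028: 23 + 396 + 16 + 49 = 484. Pro-rated: (3,506 - 484) + 484 x 5/12 = 3,022 + 202 = 3,224 (about 3,222 if counted by days). The margin over 3,195 falls from 311 to just under 30, or less than 1%.

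**The case against.** Four points can be made for the plan.

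1. **The count is not a ceiling.** A reader might infer that no more than about 1,010 patients can enter the SI cohort. The documents do not support that. Initiators are net year-on-year growth, so patients who stop and are replaced go uncounted. As an assumption, if 10% of users stop each year, replacements by April 2025 add about 10% x (29 + 346 + 805/3) = 64, where 29 and 346 are the patients exposed in 2022 and 2023; 20% adds about 129. That gives roughly 1,075 to 1,140. Section 10.3.1.2 expects low discontinuation. The forecast also keeps only the 78% of patients with non-renal or mild renal disease, although Section 10.9 does not exclude lupus nephritis. Equal uptake in the omitted 22% would give 1,012/0.78 = 1,297, but severe active nephritis lies outside the indication. Either effect alone stays below 1,312; both at full strength could pass it. The protocol quantifies neither.

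2. **Some selection is already applied.** It would be wrong to call these counts all anifrolumab users. Table 27 is restricted to treated, non-renal, moderate-to-severe SLE. What remains unapplied is the flare requirement, the 12-month look-back, prior malignancy, recent serious infection, the other SI exclusions and exposure sets dropped for positivity. These pull the count down, again by an unstated amount.

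3. **Contingencies exist.** Section 7 makes the final reports conditional on reaching the sample sizes. Sections 10.4 and 10.5.2 allow added data sources, a longer study period and revised milestones. The Table 3 end dates are marked for adaptation by country. This limits the consequence but does not correct Table 8. The checks named in Section 10.5.2 fall on 31 May 2026 and 31 May 2027, after SI enrolment has closed, and they test uptake; the mismatch would remain even if uptake were exactly as forecast. Footnote 8 calls the estimates conservative only because the data sources report slightly more SLE patients than assumed.

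4. **Even accrual is an assumption.** This is so, but rising uptake would put fewer than a third of the 2025 initiators in the first four months.

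**Conclusion.** The point stands for serious infections. The 1,435 covers eight months in which no SI patient can be enrolled. On Table 27 counted to 30 April 2025, the expected number is about 1,012 under even accrual, with 958 and 1,033 under the two alternatives shown. All are below 1,312, the first by about 23%. In the design scenario power is about 0.72 by Table 12 (0.74 by simulation) instead of 0.80; with SD 0.1 it is about 0.79. These power figures keep the plan's 2-year average follow-up, event rate and 1:3 matching. The loss is material but moderate.

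The conclusion is that the feasibility statement does not follow from the protocol's own counts. It is not a prediction of final enrolment, because unquantified effects act in both directions.

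A reader might extend the failure to malignancy. The documents do not support that: the pro-rated count still exceeds 3,195, although by less than 1% before the remaining exclusions. Nor is 3,195 a cliff, since Table 10 (6.31 per 1000 person-years, HR 1.5, SD 0.2) gives power of 0.780 at 3,000 and 0.814 at 3,500.

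**What to change.** - Recompute the SI column of Table 8 to the Table 3 enrolment end date. Give a range, and state the accrual pattern assumed within 2025, the attrition from the criteria not yet applied, and the treatment of replaced users and renal patients.
- Correct the statements in Sections 7 and 10.5.2 that the required SI size will be attained or that the SI milestone can reasonably be met.
- Then either restate SI power for the recomputed number (about 0.72 in the design scenario at about 1,012) or reconcile the SI enrolment and study end dates with the count. The data are secondary, so the enrolment end is a data cut-off; the sponsor would need to show that a later one fits the data lags and the SI report due on 30 November 2028.
- Show the malignancy count to 31 May 2028 (about 3,222 to 3,224) in Table 8 as well.

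The first, second and fourth items cost only table and wording changes, with a less favourable feasibility statement. Moving the SI dates would be a protocol amendment with possible effects on milestones.

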10.5.2 Minimum sample size required

As the main analysis for the primary outcomes (i.e., serious infections and malignancies) will involve a meta-analysis pooling the estimates across all data sources, a meta-analytic approach in sample size estimation was used for each outcome separately. Simulations were used to compute the estimated power to detect pre-specified HR values representing the average population treatment effect (mean) for the anifrolumab exposed group compared to the unexposed group for pre-specified sample sizes. In addition, the minimum sample sizes required to achieve 80% power under specific assumptions were estimated.

⁸ The number of SLE patients provided by the data sources is slightly higher than the estimated average. Thus, current estimates are expected to be a conservative measure of the number of included patients. At the time of interim reports, the number of SLE patients and the assumptions of anifrolumab uptake will be assessed to address the need of protocol adjustments to meet the necessary sample size.

Assumptions and parameters

The main objective of this study is to estimate and compare the risks between the study cohorts in terms of two outcomes – serious infections and malignancies.

Keeping this in mind, the sample analysis methodology relies on estimating power to detect any treatment associated risks between the study cohorts. In this case, we assumed pre-specified HR values of 1.5, 1.8 and 2, as the average population treatment effect (mean) and for variability of this HR, we use two values of assumed standard deviation, 0.1 and 0.2. The idea here is to have a population-level treatment effect distribution of HR with mean values of 1.5 or 1.8 or 2.0, such that from this distribution, every data source randomly samples a unique HR value per simulation run. This approach ensures the variability and heterogeneity which we expect to see from data sources which then necessitates the use of random effects meta-analysis to account for them during the final analysis of this study. Two matching ratios of exposed to non-exposed, 1:1 and 1:3, were chosen. Background rates for the primary outcomes were also varied based on published literature of incidence in the general population and in an SLE population.

Background rates

Computations were carried out with two conservative incidence rates for each outcome. Results using the incidence rates in the general population can be considered as a lower bound for the achieved power/minimum required sample sizes. Results using the incidence rates in SLE population can be considered as an upper bound for the achieved power/minimum required sample sizes.

For the malignancy outcome: There are several estimates for incidence rates (IR) of malignancy in the literature. Since this study involves cohorts situated within Europe, IR estimates based on data available within Europe for the general population and an SLE specified population were used (Table 9 and Table 10, respectively).

- Based on data from the European Cancer Information System, in 2012 the overall incidence of malignancy in the general population was 5.26 per 1000 person-years in the UK [31].
- In a multicentre study of a patient cohort from the Systemic Lupus Erythematosus Registry of the Spanish Society of Rheumatology, IR for malignancy in patients with SLE was 6.31 per 1000 person-years [19].

For the serious infection outcome: There are several estimates for IRs of serious infection in the literature. Since this study involves cohorts situated within Europe, we used IR estimates based on data available from Europe. The IR estimates in the general population and in SLE patients specified below were used for the power calculations (Table 11 and Table 12).

• In a study from the Swedish Lupus Linkage cohort, newly diagnosed patients with SLE (2006–2013) and general population comparators were followed for serious infection until

2016. Rates of serious infections in the general population were 9.6 per 1000 person-years and 39.8 per 1000 person-years amongst SLE patients [81]. The definition used for serious infection outcome in this study was hospitalisation with infection as the primary diagnosis using ICD codes from the National Patient Registry of Sweden inpatient database.

Simulation steps

For a given matching ratio (exposed: non-exposed) and a given IR, simulations were carried out for a range of overall exposed sample sizes (total sample size of exposed patients across data sources). For each overall sample size (e.g., n = 3000 exposed patients), a proportion of the overall population (country-level sample size) was assigned to each data source (proportions are presented in Table 13). These proportions are based on estimated final sample sizes for the different data sources given the relative sizes of each data source and the prevalence of SLE in each study country. The SLE prevalence in each data source was obtained by literature review (see references in Table 13) The following steps were repeated 1,000 times to get 1,000 simulated 95% CIs for HRs.

Using the simsurv package, survival times were simulated for each data source from a Weibull distribution assuming proportional hazards. The average population-level treatment effect chosen was from a pre-specified list of values -1.5, 1.8 or 2 with assumed variances of SD(HR) = 0.1 and 0.2. The provided sample sizes were taken as the exposed sample size and the non-exposed sample size was calculated as matching ratio * country-level sample size. The average follow-up times were 2 years for serious infections and 5 years for malignancies.

The estimated data source level log(HRs) for exposure status, standard errors and 95% CI were computed by fitting a cox proportional hazards model to the simulated data. The data source level log(HRs) and their standard errors were entered in a random-effect meta-analysis model to compute the pooled HR and its 95% CI. The inverse-variance method was used with the R meta package.

Finally, the proportion of 1,000 simulated runs where the meta-analysis p-value < 0.05, representing the power, was computed. Power was estimated for each pre-specified sample size of exposed group under two different outcome-specific IRs and two allocation ratios (1:1 and 1:3) for three assumed average treatment effects, HRs – (1.5, 1.8 and 2) (Log(HR) values of 0.405, 0.588 and 0.693 in lognormal space respectively) with SD[HR)] – 0.1 (expressed as the geometric coefficient of variation of log(HR) - 0.066, 0.056, 0.05 for three HRs respectively) and 0.2 (expressed as the geometric coefficient of variation of log(HR) - 0.132, 0.11, 0.099 for three HRs respectively In addition, the exact sample size required to achieve 80% power was estimated (Table 13).

The tables below show the power achieved for different pre-specified sample size values for the two main outcomes – serious infections (Table 9 and Table 10) and malignancy (Table 11 and Table 12) obtained from the simulation as described above.

Table 9	Meta-analys	is level powe	r to detect pi	re-specified t	arget HR un	der different	study
size and	assumptions	s of malignan	icy incidence	– allocation	ratio 1:1		
Malignancy	Number of	Power for	Power for	Power for	Power for	Power for	Power for

Malignancy	Number of	Power for					
IR	exposed to	detecting a					
	anifrolumab	HR of 1.5 &	HR of 1.5 &	HR of 1.8 &	HR of 1.8 &	HR of 2 &	HR of 2 &
		SD(HR)	SD(HR)	SD(HR)	SD(HR)	SD(HR)	SD(HR)
		=0.1	=0.2	=0.1	=0.2	=0.1	=0.2
	500	0.122	0.152	0.284	0.279	0.390	0.395
	1000	0.263	0.287	0.542	0.548	0.687	0.680
	1500	0.421	0.381	0.697	0.657	0.813	0.811
	2000	0.477	0.483	0.772	0.756	0.864	0.851
5.26 per	2500	0.554	0.507	0.843	0.809	0.926	0.897
1000	3000	0.621	0.579	0.874	0.843	0.928	0.914
person-years	3500	0.679	0.638	0.902	0.889	0.955	0.951
	4000	0.717	0.669	0.922	0.903	0.961	0.960
	4500	0.762	0.710	0.938	0.934	0.988	0.983
	5000	0.811	0.788	0.955	0.962	>0.999	>0.999
	5500	0.852	0.833	0.961	>0.999	>0.999	>0.999
	500	0.179	0.169	0.334	0.325	0.474	0.463
	1000	0.309	0.332	0.624	0.584	0.794	0.740
	1500	0.439	0.428	0.765	0.741	0.882	0.842
6.01	2000	0.561	0.531	0.816	0.808	0.903	0.910
6.31 per	2500	0.632	0.570	0.872	0.869	0.936	0.918
1000 person-years	3000	0.662	0.622	0.899	0.899	0.954	0.939
person-years	3500	0.731	0.663	0.923	0.922	0.962	0.958
	4000	0.761	0.717	0.941	0.944	0.988	0.977
	4500	0.811	0.794	0.975	0.957	0.991	>0.999
	5000	0.847	0.829	0.991	0.976	>0.999	>0.999

Abbreviation – HR: hazard ratio; IR: incidence rate; SD: standard deviation

Table 10 Meta-analysis level power to detect pre-specified target HR under different study size and assumptions of malignancy incidence – allocation ratio 1:3

Malignancy IR	Number of exposed to anifrolumab	Power for detecting a HR=1.5 &SD(HR) =0.1	Power for detecting a HR of 1.5 & SD(HR) =0.2	Power for detecting a HR of 1.8 & SD(HR) =0.1	Power for detecting a HR of 1.8 & SD(HR) =0.2	Power for detecting a HR of 2 & SD(HR) =0.1	Power for detecting a HR of 2 & SD(HR) =0.2
	500	0.310	0.364	0.581	0.631	0.735	0.729
	1000	0.497	0.503	0.768	0.792	0.901	0.870
5.26 per	1500	0.629	0.610	0.881	0.852	0.933	0.935
1000	2000	0.670	0.683	0.933	0.897	0.967	0.969
person-years	2500	0.762	0.701	0.938	0.936	0.978	0.978
	3000	0.786	0.754	0.956	0.944	0.985	0.979
	3500	0.818	0.781	0.969	0.959	0.994	0.991

Anifrolumab, EMEA/H/C/004975, Serious Infections & Malignancies PASS

Malignancy IR	Number of exposed to anifrolumab	Power for detecting a HR=1.5 &SD(HR) =0.1	Power for detecting a HR of 1.5 & SD(HR) =0.2	Power for detecting a HR of 1.8 & SD(HR) =0.1	Power for detecting a HR of 1.8 & SD(HR) =0.2	Power for detecting a HR of 2 & SD(HR) =0.1	Power for detecting a HR of 2 & SD(HR) =0.2
	4000	0.853	0.795	0.981	0.975	0.991	0.991
	4500	0.883	0.818	>0.999	>0.999	>0.999	>0.999
	500	0.362	0.358	0.642	0.658	0.785	0.783
	1000	0.555	0.511	0.835	0.817	0.914	0.911
	1500	0.657	0.632	0.915	0.902	0.959	0.955
6.31 per 1000	2000	0.723	0.694	0.938	0.920	0.979	0.963
person-years	2500	0.781	0.763	0.968	0.937	0.986	0.981
person years	3000	0.841	0.780	0.971	0.959	0.986	0.988
	3500	0.879	0.814	0.983	0.980	0.994	0.995
	4000	0.888	0.815	0.984	0.979	0.997	0.996

Abbreviation - HR: hazard ratio; IR: incidence rate; SD: standard deviation

Table 11 Meta-analysis level power to detect pre-specified target HR under different study
size and assumptions of serious infections incidence – allocation ratio 1:1

Serious	Number of	Power for					
Infections	exposed to	detecting a					
IR	anifrolumab	HR of 1.5 &	HR of 1.5 &	HR of 1.8 &	HR of 1.8 &	HR of 2 &	HR of 2 &
		SD(HR)	SD(HR)	SD(HR)	SD(HR)	SD(HR)	SD(HR)
		=0.1	=0.2	=0.1	=0.2	=0.1	=0.2
9.6 per 1000 person-years	500	0.087	0.099	0.161	0.165	0.288	0.304
	1000	0.192	0.218	0.418	0.433	0.548	0.553
	1500	0.289	0.305	0.590	0.599	0.749	0.731
	2000	0.377	0.368	0.711	0.675	0.811	0.803
	2500	0.433	0.426	0.762	0.719	0.871	0.854
	3000	0.529	0.484	0.819	0.791	0.903	0.875
	3500	0.560	0.509	0.838	0.817	0.926	0.902
	4000	0.617	0.566	0.879	0.857	0.936	0.932
	4500	0.689	0.697	0.901	0.881	0.966	0.956
	5000	0.761	0.754	0.959	0.948	>0.999	0.977
	5500	0.822	0.804	>0.999	0.982	>0.999	>0.999
39.8 per 1000 person-years	500	0.375	0.392	0.665	0.692	0.809	0.804
	1000	0.635	0.582	0.885	0.851	0.945	0.930
	1500	0.732	0.710	0.946	0.925	0.978	0.968
	2000	0.825	0.771	0.975	0.948	0.987	0.985
	2500	0.868	0.826	0.973	0.968	0.996	0.987

Abbreviation - HR: hazard ratio; IR: incidence rate; SD: standard deviation

size and assumptions of serious infections incidence – allocation ratio 1:5									
Serious	Number of	Power for							
Infections	exposed to	detecting a							
IR	anifrolumab	HR of 1.5 &	HR of 1.5 &	HR of 1.8 &	HR of 1.8 &	HR of 2 &	HR of 2 &		
	SD(HR) SD(HR) SD(HR) SD(HR) SD		SD(HR)	SD(HR)					
		=0.1	=0.2	=0.1	=0.2	=0.1	=0.2		
	500	0.265	0.256	0.474	0.516	0.621	0.617		
	1000	0.409	0.433	0.716	0.706	0.832	0.813		
	1500	0.520	0.500	0.813	0.779	0.897	0.902		
0.6 1000	2000	0.586	0.606	0.876	0.854	0.955	0.937		
9.6 per 1000 person-years	2500	0.662	0.644	0.905	0.893	0.958	0.955		
person-years	3000	0.714	0.657	0.930	0.908	0.976	0.972		
	3500	0.750	0.722	0.962	0.923	0.985	0.972		
	4000	0.800	0.753	0.965	0.941	0.985	0.974		
	4500	0.816	0.801	0.971	0.964	>0.999	>0.999		
39.8 per	500	0.583	0.569	0.852	0.829	0.943	0.925		
1000	1000	0.789	0.716	0.958	0.947	0.981	0.985		
person-years	1500	0.882	0.835	0.977	0.975	0.995	0.987		

Table 12 Meta-analysis level power to detect pre-specified target HR under different study size and assumptions of serious infections incidence – allocation ratio 1:3

Abbreviation - HR: hazard ratio; IR: incidence rate; SD: standard deviation

For the malignancy outcome, using an allocation ratio of 1:3, an average follow-up time of 5 years, and an IR of 6.31 per 1000 person-years, the minimum required sample size to achieve 80% power for detecting a pre-specified true HR of 1.5 (geometric mean of 0.425 in lognormal space) from an effect distribution with SD(HR) of 0.2 (geometric coefficient of variation of 0.132 in lognormal space), is approximately **3,195** anifrolumab patients across all countries.

For serious infections, using an allocation ratio of 1:3, an average follow-up time of 2 years, and an IR of 39.8 per 1000 person-years, the minimum required sample size to achieve 80% power for detecting a pre-specified true HR of 1.5 (geometric mean of 0.425 in lognormal space) from an effect distribution with SD(HR) of 0.2 (geometric coefficient of variation of 0.132 in lognormal space), is approximately **1,312** anifrolumab patients across all countries.

The proportional share for each data source was based on the expected number of SLE patients as presented in section 10.5.1. These proportions along with the required country-level sample size to achieve 80% power to detect a pre-specified HR of 1.5 (geometric mean of 0.405 in lognormal space) from an effect distribution with SD(HR) of 0.2 (geometric coefficient of variation of 0.132 in lognormal space) with a 1:3 matching is presented in Table 13.

Considering the estimated number of patients initiating anifrolumab during the study period (3,506 for the malignancies cohort, and 1,435 for the serious infections cohort Table 8) and the required sample size presented above (3,195 for the malignancies cohort and 1,312 for the serious infections

cohort), there is a reasonable assumption that the final study report milestones as specified in this protocol can be met. However, the assumptions used in the calculation of the exposed anifrolumab patients will be evaluated at the first progress report (31 May 2026) and first interim report (31 May 2027). If the assumptions do not hold, the final study report milestones will be re-evaluated, and potential mitigation steps will be explored.

each data source)											
Country	Share of	Minimum required sample size	Minimum required sample size								
	country in	(anifrolumab patients) for the	(anifrolumab patients) for the SI								
	study (%)	Malignancy outcome with IR = 6.31	outcome with IR = 39.8 per 1000 py								
		per 1000 py									
Denmark	5.89%	188	77								
France	74.56%	2,382	978								
Germany	5.40%	173	71								
Spain	14.16%	452	186								
Total	100.00%	3,195	1,312								

Table 13 Minimum sample size needed for malignancy and SI outcomes (overall and in each data source)

Abbreviation - HR: hazard ratio; IR: incidence rate; SD: standard deviation

